Preliminary data relevant for the current proposal derive from our Merck-funded hot flash-related insomnia study of psychological and physiological arousal in midlife women, all of whom have hot flashes but only some of whom meet criteria for a concurrent insomnia syndrome. Eligibility criteria for women meeting criteria for an insomnia syndrome included a minimum of 20 minutes of time for subjective WASO (sWASO) plus subjective sleep-onset latency (sSOL) together, but there was no requirement for a maximum total sleep time (sTST) or minimum Insomnia Severity Index (ISI) score. At the time when this current protocol was developed, we had enrolled 73% of our total accrual goal of 40 participants. Of 29 women who had consented, data were available on 23 who had already completed study procedures. Of those who met criteria for an insomnia syndrome (n=17), 6 (35%) had an ISI score ≥ 15 , consistent with eligibility criteria for the proposed trial. As such, we report interim findings for this subgroup based on sleep parameter data obtained using a 7-day sleep diary and actigraphic assessment. This subgroup showed a mean ISI score of 18.8 ± 1.7 and a mean sleep efficiency of $66.8\% \pm 31.8\%$ on the diary and $81.9\% \pm 8.9\%$ on actigraphy.

Sleep maintenance problems characterize hot flash-related insomnia: Those who would be eligible for the proposed trial report experiencing 128.7 ± 67.9 minutes of sWASO and 34.7 ± 15.4 minutes of sSOL on their diary. sWASO time comprises 78.8% of the total wake time (sWASO+sSOL). All of these women would meet our proposed eligibility criterion of sWASO ≥ 30 minutes). This observed predominance of sleep maintenance problems is consistent with our prior experience^{7,19,20} and with extensive epidemiologic data^{3,21} on hot flash-related sleep disruption. Data using actigraphy to quantify WASO and SOL similarly indicate that aWASO time accounts for the vast majority (78.7%) of wakefulness (aWASO+aSOL). Consistent with extensive data from other insomniac populations,²² the total number of minutes of aWASO and aSOL on actigraphy is reduced relative to that reported on the diary. However, the actigraphic aWASO is consistent with our planned 30 minute average of WASO, with 100% of these women having at least 30 minute average of WASO over a week.

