Total sleep time is reduced in women with hot flash-related insomnia: Despite an absence of TST eligibility criteria, 100% of women in our physiologic study who would meet criteria for the proposed trial also meet our similar criterion to have subjective TST (sTST) < 7 hours both on sleep diary and on actigraphy during at least 4 nights per week.

Distribution of WASO time across the night in hot flash-related insomnia: Further analyses of actigraphic data in this subgroup of women who would be eligible for the proposed trial show that 36.9% of their aWASO time occurs within the terminal one-third of the night.

Within-person night-to-night variability in sleep parameters: It is increasingly recognized that sleep patterns vary night-to-night in insomniacs, on both sleep diary²³ and at-home polysomnography (PSG)²⁴ measures. We explored this within-person variability across the 7 consecutive days of sleep diary and actigraphic monitoring in the subgroup of women who would be eligible for our proposed study. The coefficients of variation (CV) show that there is limited within-person night-to-night variability in SOL or WASO as a proportion of the respective mean value for each person, regardless of whether they were measured using the sleep diary (sSOL, sWASO) or actigraphy (aSOL, aWASO). For the group as a whole, the mean CV for each sleep parameter was less than or close to one, indicating limited variation.

Hot flash-related insomnia and psychological indicators of hyperarousal: In our investigation examining the association between hyperarousal and insomnia in women with hot flashes, we have observed a pattern of greater psychological arousal among women with hot flashes that is proportionate to the amount of sleep interruption. As one indicator of psychological activation in the sample overall (n=23), those who had more anticipatory anxiety also had more sWASO ($r_s=0.48$, $p=0.02$).

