Summary of preliminary data: Taken together these preliminary data highlight that for women with hot flash-related insomnia syndromes who would be eligible for our proposed trial: 1) the extent of their sleep disturbance is high, 2) sleep maintenance problems dominate the time spent awake, and 3) WASO time persists into the final third of the night. In addition, within-person night-to-night variability of SOL and WASO is low on both subjective and actigraphic measures. In addition, psychological indicators of hyperarousal correlate with the degree of sleep disruption among women with hot flashes. *In summary, women with a hot flash-related insomnia syndrome have substantial sleep continuity problems that are composed of a distinctive profile of sleep disruption dominated by reduced TST and large amounts of WASO, which persists throughout the night. These characteristics of hot flash-related insomnia make this population an ideal one in whom to investigate the efficacy of suvorexant.*

II. SPECIFIC AIMS

PRIMARY AIM: To determine the effect of suvorexant on insomnia symptoms in peri- and postmenopausal women with a chronic insomnia syndrome related to nighttime hot flashes using a randomized placebo-controlled trial.

HYPOTHESIS: Women randomized to suvorexant will show greater improvement in insomnia symptoms compared with women randomized to placebo.

SECONDARY EXPLORATORY HYPOTHESES

1. Relative to those assigned to placebo, women randomized to suvorexant will show:
 - a. Greater reduction in wake-time after sleep-onset.
 - b. Greater improvement in mood, anxiety, and quality of life.
 - c. Greater reduction in hot flash frequency.
2. Improvement in insomnia symptoms will be positively correlated with improvement in mood, anxiety, hot flashes, and quality of life.

III. SUBJECT SELECTION

Inclusion/Exclusion Criteria

We plan to enroll up to 90 women who meet the following criteria in order to have 72 women randomized in a 1-to-1 ratio to suvorexant 10-20 mg or equivalent placebo in order to have 60 women (30 per arm) complete the trial.

Inclusion criteria:

1. Age 40–65 years
2. Peri- or postmenopausal women, with menopause status determined by menstrual marker. Women who underwent bilateral oophorectomy will be enrolled if 6+ months from surgery. Those who underwent hysterectomy with ovarian preservation, or who have amenorrhea from progesterone-secreting IUD, or endometrial ablation may be enrolled based on clinical assessment and judgment.

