3. DSM-5 criteria for Insomnia Disorder.

4. Score on the Insomnia Severity Index (ISI) measure ≥ 15 , indicating at least a moderate level of insomnia symptoms
5. Subjective sleep disruption reported retrospectively over the past month and confirmed prospectively on a 7-day sleep diary shows:
 - a. < 9 hours average for subjectively reported total sleep time (TST).
 - b. 30+ minute average for subjectively reported wake after sleep onset (sWASO).
 - c. Sleep parameter in inclusion criteria 5a does not decrease by more than 50% on a 2nd week of sleep diary monitoring obtained after the screening visit.
 - d. Sleep parameter in inclusion criteria 5b does not both decrease by more than 50% and fall below 30 minutes on average on a 2nd week of sleep diary monitoring obtained after the screening visit.
6. Average of 2 or more hot flashes per 24 hours, at least some of which occur each night, reported retrospectively to have occurred over the past month and confirmed prospectively on one 7-day hot flash diary
7. Subjective report that at least some awakenings co-occur with night time hot flashes.

Exclusion criteria:

1. Sleep factors:
 - a. Diagnosis, or strong clinical suspicion, of other primary sleep disorders: obstructive sleep apnea, periodic limb movement disorder, narcolepsy, or RLS
 - b. Shift workers
 - c. Use of hypnotic medications more than twice per week in the past month
 - d. Willingness to not use other sedative-hypnotics during the study period
2. Psychiatric factors:
 - a. Current major depressive episode, by report and as indicated by the Patient Health Questionnaire (PHQ-9)
 - b. Current suicidal ideation
 - c. Lifetime history of bipolar disorder, psychosis, or other serious mental health problem
 - d. Current alcohol/substance use disorder
3. Medical factors:
 - a. Abnormal vital signs at screening visit
 - b. BMI ≥ 40 kg/m²
 - c. Renal or hepatic disease judged to interfere with drug metabolism and excretion
 - d. Pregnancy or breastfeeding
 - e. Malignancy within past 2 years
 - f. Major surgery within past 3 months
 - g. Neurological disorder or cardiovascular disease raising safety concerns about use of suvorexant and/or judged to interfere with ability to assess efficacy of the treatment
 - h. Medical instability considered to interfere with study procedures
 - i. Concomitant medications with drug interaction or co-administration concerns
 - j. Contraindications or allergic responses to suvorexant
4. Lifestyle and other factors:

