Women interested in participating in this trial will be screened by phone to assess preliminary eligibility after oral consent for screening is obtained. Some questions from the Berlin Questionnaire will be administered to screen for sleep apnea, and the ISI will help assess eligibility. Those who are interested and appear eligible will be sent a 7-day sleep and hot flash diary. Subjects who are taking any medications to help them sleep will be asked if they are willing to suspend taking those medications for the duration of the study, beginning with the tracking period, in order to attain an accurate assessment of their current sleep difficulties. Upon receiving these completed diaries, those who meet further eligibility criteria determined by the diaries (see Inclusion and Exclusion Criteria above) will be scheduled for an in-person Screening Visit.

At the Screening Visit, written informed consent will be obtained and final eligibility criteria will be assessed, including a clinical interview conducted by a study clinician to diagnosis a chronic insomnia disorder and to ensure that women with contraindicated sleep, medical, and psychiatric problems and medications are excluded. Vital signs will be obtained and blood will be drawn (15mL) for screening safety labs, a toxicology screen, and female reproductive hormones. The PHQ-9 will be administered in person. All women who sign the consent form will be assigned a study identification number regardless of eligibility status. Eligible participants will be sent home with a 7-day sleep and hot flash diary to complete during the screening run-in period. They will also be given the Actiwatch actigraphic monitor and Biolog skin conductance hot flash monitor, which will be worn continuously for one week (Actiwatch) or one 24-hour period (Biolog) to quantify sleep patterns (Actiwatch) and the number of objectively measured nighttime and daytime hot flashes (Biolog). No medication will be provided. They will be asked to bring their diaries, Actiwatch, and Biolog monitors back for review at the Randomization Visit, at which point final review of the sleep diary and laboratory results for definitive eligibility will be conducted before the participant is randomized to treatment.

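### Inclusion 5c runs against the limit it refers to: 5a caps total sleep time, but 5c fails only a fall of more than 50% and passes any rise (minor)

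*Combined protocol and SAP*

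**What the plan says.** All the operative text is in Section III, Inclusion criteria, item 5.

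- **5a** sets an upper limit on the diary average: "< 9 hours average for subjectively reported total sleep time (TST").
- **5b** sets a lower limit of 30 minutes on average diary wake after sleep onset (sWASO).
- **5c** is the second-week rule for the 5a parameter: "Sleep parameter in inclusion criteria 5a does not decrease by more than 50% on a 2nd week of sleep diary monitoring". It names no limit.
- **5d** is the second-week rule for the 5b parameter. It requires that sWASO "does not both decrease by more than 50% and fall below 30 minutes on average".

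The second diary week follows the screening visit. Section V (Screening period) says that "final review of the sleep diary and laboratory results for definitive eligibility will be conducted before the participant is randomized to treatment".

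Section I (Preliminary Data) also treats a TST criterion as a ceiling; of the earlier study it says that "there was no requirement for a maximum total sleep time (sTST"). It describes a similar TST criterion for this trial as "< 7 hours both on sleep diary and on actigraphy during at least 4 nights per week", which differs from 5a in both the limit and the measure. The summary of those data characterises the population by "a distinctive profile of sleep disruption dominated by reduced TST and large amounts of WASO".

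**The concern.** For a parameter with an upper limit, a woman stops qualifying when her value rises. 5c acts only when it falls. Read literally, it can turn away a woman whose sleep has become much shorter since the first diary, and it puts no check on one whose sleep time has recovered past the entry limit. 5d, the companion rule, does run in the direction of improvement: falling wake time is better sleep.

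This is an operative eligibility rule, applied after consent and before randomisation. What is at stake is which women are randomised, and whether staff who apply the presumed intent depart from the written text.

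**Working it through.** **1. Direction (no assumptions).** Let T1 and T2 be average TST in diary weeks 1 and 2. 5a requires T1 < 9 h, and 5c fails a woman only if T2 < 0.5 × T1. Then T2 < 0.5 × 9 = 4.5 h, so every woman who fails 5c still meets 5a, with less sleep than before.

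- 6.0 to 2.9 h: fall of 3.1/6.0 = 51.7%; fails 5c, still meets 5a.
- 6.0 to 3.0 h: fall of exactly 50%; passes 5c.
- 5.0 to 9.5 h: rise of 4.5/5.0 = 90%; passes 5c, no longer meets 5a.

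**2. A typical woman.** The Preliminary Data subgroup (n=6) reports "128.7 ± 67.9 minutes of sWASO and 34.7 ± 15.4 minutes of sSOL on their diary" and a diary sleep efficiency of 66.8%. Assume time in bed = TST + sWASO + sSOL (sSOL being diary sleep latency) and use a ratio of means. This is rough, since the efficiency SD is 31.8 points.

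- Wake time = 128.7 + 34.7 = 163.4 min.
- Time in bed = 163.4 / (1 − 0.668) = 492 min (8.2 h).
- TST = 0.668 × 492 = 329 min (5.48 h).

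She fails 5c as written only if her weekly average drops below 5.48/2 = 2.74 h.

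**3. What 5d already catches.** 5d fails sWASO below the smaller of 30 min and half the week-1 value. With 5b at 30 min or more, that cut lies between 15 and 30 min. A woman sleeping 9 h (540 min) or more therefore passes 5d only with at least 540 + 15 = 555 min (9.25 h) in bed, plus sleep latency. That is at least 63 min above the implied 492 min, so few women are likely to reach 9 h of sleep and still pass 5d.

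**4. How often each rule would bite.** The documents give no week-to-week TST data. Assumed, not from the documents: T1 and T2 bivariate normal, mean 5.0–6.0 h, between-woman SD 1.0–1.5 h, week-to-week correlation 0.5–0.85, with 2 million simulated pairs per setting. The figures are the share of women meeting the week-1 limit who would fail in week 2. The mid case is mean 5.5 h, SD 1.5 h, correlation 0.7. The 7 h column treats 7 h as a weekly average for illustration; the Preliminary Data criterion counts nights.

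| Second-week rule: fails if | 9 h limit: range (mid case) | 7 h limit: range (mid case) |
|---|---|---|
| As written: fall > 50% | 0–2.7% (0.7%) | not tabulated |
| Rise > 50%, no limit named | 0.02–10.4% (4.4%) | 0.02–11.4% (5.2%) |
| Pattern of 5d: rise > 50% and at or above the limit | 0–0.3% (0.03%) | 0–3.3% (0.7%) |
| 5a limit re-applied in week 2 | 0–1.9% (0.7%) | 1.2–17.5% (8.9%) |

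As written, 2.7% of 90 women is 2.4, so about 0 to 2 women. Women who already fail 5d are not removed from any row, so each share overstates what the rule adds to 5d.

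**5. Role of the limit.** On the 5d pattern with 9 h, the limit sets the threshold only for T1 below 9/1.5 = 6 h; from 6 h up, the 50% clause alone does. For the woman at 5.48 h, the threshold is 9.0 h (a 64% rise) with the 9 h limit, and just above 8.2 h (1.5 × 5.48) with the 7 h limit.

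**The case against.** The strongest defence is that 5c is not a persistence check at all. It could be a stability or diary-reliability check, or a deliberate exclusion of women whose sleep has collapsed. 5c and 5d already differ in form, because only 5d names a limit. The documents do not exclude this reading, so the intent behind 5c cannot be called established. But nothing in them states it either, a stability check would be expected to catch large rises too, and the stem of criterion 5 is about confirming sleep disruption prospectively. What stands is that the finding about purpose must be conditional. The direction of the text is not in doubt.

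Second, other safeguards remain: 5b, 5d, an ISI of at least 15, the DSM-5 diagnosis, and the diary review before randomisation. That review might be read as re-applying 5a to the second week, but no section says so. This objection limits the size of the problem and does not remove it.

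Three stronger readings are tempting, and the documents do not support them.

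- A reader might infer that the trial result is biased. Eligibility is settled before blinded 1:1 assignment, so the rule affects the population and not the comparison between arms.
- A reader might infer that the gap between 7 h and 9 h decides whether a corrected 5c screens anyone. That depends on the correction. With a plain reversal of direction the limit hardly matters (4.4% against 5.2% in the mid case). On the 5d pattern few women fail at either limit. The gap is large only if the limit is re-applied in week 2 (0.7% against 8.9%).
- A reader might infer that the TST entry limit is undefined. The 7 h text is background, is labelled as similar, and counts nights. 5a is the operative criterion.

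**Conclusion.** Wrong as written, and minor. That 5c can remove only women who still meet 5a, and lets through women who no longer do, follows from the text alone. That this is a reversed persistence check is an inference from the pairing with 5d.

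The effect falls on who is randomised and is probably small. The range of 0 to 2.7% for 5c as written rests wholly on the assumed mean, SD, correlation and normality. The true frequency cannot be fixed from the documents.

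**What to change.** In one amendment:

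1. Restate 5c so that its direction fits the upper limit in 5a. One form parallel to 5d is that average TST does not both rise by more than 50% and reach the 5a limit. If excluding sharply shortened sleep is intended, keep the direction and give the reason. Simply requiring 5a to be met again would be stricter than the 5d pattern: a change from 8.9 to 9.0 h would then exclude.
2. Say whether 5a is re-applied to the second diary week at the review before randomisation.
3. Reconcile the TST criterion in the Preliminary Data (below 7 h on at least 4 nights a week) with 5a (average below 9 h). The sponsor decides which stands.

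If the 9 h limit stands, the cost is wording. A tighter limit would mean screening more women to randomise 72; how many more cannot be computed from the documents.

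Two separate items can go in the same amendment, although neither supports this point. Exclusions 1d and 5a are phrased as desirable attributes and should be put in the negative, as 4d is (editorial; the intent is plain). Section VII (Reproductive Risks) excludes women who use hormones, while inclusion 2 allows women with amenorrhea from a progesterone-secreting IUD, and no Section III entry criterion names a hormone exclusion. These passages must be reconciled, and the sponsor decides which rule stands.

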answer questions will be thanked for their time and the phone call will end. Women may ask to stop the screening phone call at any time. The pre-screen questionnaires will be administered to assess insomnia status. The full written ISI will be administered at Visit 3 and Visit 4. The ISI may be administered again over the phone before Visit 1 or Visit 2, if one of these visits has been delayed, and insomnia status must be reassessed. Preliminary screening determination will include questions modified from the Berlin Questionnaire to exclude women at high risk for obstructive sleep apnea. We will also ask some questions drawn from the PHQ-9 which will be completed at the first visit. The PHQ-2 asks specifically about frequency of anhedonia and depression in the past two weeks. We will exclude participants who do not qualify initially on the phone screen. Anyone identified as being at risk for depression will be instructed to assess their symptoms with their physician and be offered resources for where they can seek additional help. The full PHQ-9 will be administered at Visit 1, Visit 3, and Visit 4.

Following the screening phone call, women who are interested and preliminarily eligible to complete the screening process will be mailed or emailed the pre-screening materials, a copy of the informed consent and a cover letter describing the pre-screening procedures. The pre-screening materials include hot flash and sleep diaries to be completed at home for 1 week. BWH study staff will call potential participants to determine whether they received these materials and review how to complete them. Women who are currently taking medications to help them sleep will be asked if they are willing to refrain from taking sleep medications for the duration of the study (approx. 6 weeks) beginning with the tracking period. Women who agree to complete the pre-screening diaries will be contacted by phone after ample time has elapsed. During this call, the BWH study staff member will review the diary entries to determine eligibility for the screening visit. The pre-screening diaries are used to reduce subject burden by only scheduling subjects eligible for the screening visit.

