Treatment period: At the Randomization Visit, eligible women will be randomized to 4 weeks of suvorexant or placebo. Pre-treatment symptom measures will be assessed at the Randomization Visit and interim and final on-treatment symptom measures will be assessed at the Interim Treatment Visit and Final Treatment Visit, respectively. The primary endpoint measures will be obtained at the Final Treatment Visit, conducted after 4 weeks on treatment. Participants will complete sleep and hot flash diaries for the 4 weeks they are on treatment and will be sent an Actiwatch and Biolog monitor to wear for one week (Actiwatch) and for one 24-hr period (Biolog) before returning them at the Final Treatment Visit. Participants will also be asked to provide saliva samples for two consecutive days in between Visits 1 and 2 and Visits 3 and 4. These samples will be used to measure cortisol. We have implemented these procedures in prior clinical trials

with efficiency and high levels of adherence. Adverse events will be assessed at each study visit using spontaneous-reporting adverse event procedures employed in our other clinical trials.

Intervention design: Suvorexant and identical placebo will be obtained from Merck and stored in the Brigham and Women’s Hospital Research Pharmacy. The Research Pharmacist will generate a confidential randomization schema using a block size of 4 to balance the one-to-one treatment assignment between the two study arms. Study participants and all study personnel, including those entering data, will be blinded to the assignment. Only the Research Pharmacist will be unblinded to treatment assignment.

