Biolog skin conductance hot flash monitor: This is a widely used and validated ambulatory skin conductance monitor (UFI, Morro Bay, CA) that will be worn to quantify the number of objectively measured hot flash events by detecting changes in skin conductance on the sternum. This approach measures physiologic hot flashes independent of recall for the events, thereby eliminating potential recall bias for nighttime events.

Surgical Interventions

No surgical interventions will be used in this study.

VI. BIostatistical Analysis

Overview of analytic plan: The primary hypothesis for this trial is that suvorexant is superior to placebo in treating insomnia symptoms. The primary endpoint is the change in the ISI score from

baseline to 4-week follow-up. Exploratory analyses will examine the effect of suvorexant relative to placebo on secondary endpoints of sleep continuity parameters and diary-reported hot flashes, and exploratory endpoints including mood, anxiety, hot flashes (skin-conductance monitor), physiological stress (salivary cortisol), and quality of life.

Study endpoints:

Primary endpoint:

1. The primary endpoint is the change in the ISI score from baseline to 4-week follow-up.

Secondary endpoints:

1. Diary-reported WASO, SOL, TST, and sleep efficiency
2. Number of hot flashes reported on the diary separately during the day and night

Exploratory endpoints:

1. Actigraphy-measured WASO, SOL, TST, and sleep efficiency
2. Depressive symptoms
3. Anxiety symptoms
4. Quality of life
5. Number of hot flashes measured on the skin-conductance monitor
6. Physiological Stress (measured by salivary cortisol)

Primary analysis: The primary analysis will compare the within-person change in outcomes at Week 4 relative to baseline using general linear models, adjusting for baseline values and relevant covariates showing group differences at baseline. Diagnostic methods will be used for all models to assess their distributional assumptions, model adequacy, and to examine potential outlying or influential data points. An additional exploratory ISI responder analysis will be conducted using logistic regression to determine whether there is a group difference in the proportion of women that had a 8-point reduction in the ISI score from baseline.⁴¹

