Missing data: Every effort will be made to avoid missing data and to include all randomized subjects in the analysis. The effects of missing information on statistical power have been addressed to the degree feasible in the sample size calculations. Missing data will be imputed as last observation carry forward.

Power and sample size: In total, up to 90 women will be enrolled in this study. Treatment will be randomly assigned in a 1:1 ratio. Allowing for 10% to be lost to follow up after consent (n=8) and 15% to be lost after randomization (n=12), we expect to randomize up to 72 participants to treatment and complete 60 subjects (30 per treatment group). This sample size provides enough subjects to have 80% power for the primary hypothesis, assuming that there is a between-group difference in the change from baseline to study-end in the ISI score of 4 points with a standard deviation of 4.86 (two-sided alpha = 0.05). Previous clinical trials have found between-group differences in ISI change scores of 5.2 points¹¹ when women with hot flash-related insomnia were randomized to CBTi vs. behavioral control and between-group differences in ISI change scores of 2–3 points⁴³ when women with hot flashes and sleep disturbance were randomized to the SSRI citalopram vs. placebo. The standard deviation in the change in ISI for these interventions and controls arms was selected because it is in the midpoint of standard deviations from previous studies, which ranged from 4 to 6.^{11,43} Data from the Phase 3 suvorexant trials were not used to support our sample size calculations because of differences in the sleep profile between our hot flash-related insomnia population (see Preliminary Data) and the general insomnia population

enrolled in suvorexant trials for which there was no minimum ISI score required for eligibility (mean ISI ~14).⁴⁴

VII. RISKS AND DISCOMFORTS

Potential risks of study procedures:

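### Does the written-ISI schedule in Section IV leave the primary endpoint without a usable baseline?

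*Combined protocol and SAP*

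**What the plan says.** Section VI defines the endpoint: "The primary endpoint is the change in the ISI score from baseline to 4-week follow-up". It names no visit for baseline. The model compares change at Week 4 "using general linear models, adjusting for baseline values and relevant covariates showing group differences at baseline", so the baseline ISI enters both the outcome and the covariate.

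The ISI schedule appears in three places:

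- **Section IV, Pre-Screening:** "The full written ISI will be administered at Visit 3 and Visit 4". The same paragraph adds: "The ISI may be administered again over the phone before Visit 1 or Visit 2, if one of these visits has been delayed".
- **Section V, Table of Procedures:** the ISI is marked at Pre-V1 (phone and mail), V2 (randomisation), V3 and V4, and is blank at V1. V2 is shown at 0 weeks on medication, V3 at 1 week and V4 at 4 weeks.
- **Section V, Treatment period:** "Pre-treatment symptom measures will be assessed at the Randomization Visit", with the primary endpoint measures taken at the Final Treatment Visit.

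On the telephone score, the Screening period text in Section V says "the ISI will help assess eligibility".

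**The concern.** Taken literally and alone, the Section IV sentence gives no written ISI before the first dose. Baseline would then be a telephone score, and that score also helps select women at ISI 15 or more. Three consequences would follow.

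- Selection on a noisy score brings regression to the mean into every change score, which inflates apparent improvement and the 8-point responder rate in both arms.
- The telephone score is older than a V2 score. By the table's study weeks it lies about 6 weeks before V4 (week -1 to week 5), against 4 weeks for V2 (week 1 to week 5). A weaker correlation with Week 4 would cost precision.
- Some women could have a repeated telephone score and others not, so baselines would differ in age, and in mode from the written follow-up.

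This is the only primary endpoint, so an undefined baseline deserves a check.

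**Working it through.** **1. Which ISI does the plan supply before dosing?**

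| Source | Pre-dose ISI | Stated purpose |
|---|---|---|
| Section IV, Pre-Screening | Telephone only; repeated if Visit 1 or 2 is delayed | Checking insomnia status |
| Section V, Screening period | Telephone | Eligibility |
| Section V, Table of Procedures | Pre-V1 and V2 | Scheduled assessments |
| Section V, Treatment period | Randomisation visit (symptom measures in general) | Pre-treatment measurement |

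Section V refers the reader to the table for the full set of procedures. The Section IV sentence sits in an account of telephone screening and does not say that the ISI is given at no other visit. No section calls a telephone score a baseline. Following the whole plan yields a V2 ISI at zero weeks on medication.

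**2. The plan's own power figure.** Inputs from Section VI: difference 4, SD of change 4.86, two-sided alpha 0.05, 30 completers per arm, stated power 80%.

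Power = Φ(δ / (σ√(2/n)) − 1.96) = Φ(4 / (4.86 × √(2/30)) − 1.96) = Φ(3.19 − 1.96) = 89%. A two-sample t-test calculation gives 88%, and 80% needs about 24 per arm. The stated 80% is therefore met with room to spare.

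**3. Cost if the telephone score were used after all.** Assumptions not in the documents: score SD s = 4.86 at both times, and baseline-to-Week-4 correlation ρ = 0.5 for V2, which reproduces the planned SD of change because s√(2(1−ρ)) = 4.86. For a telephone baseline, take ρ from 0.4 down to 0.2. The baseline-adjusted SD is s√(1−ρ²).

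| ρ | SD, unadjusted change | Power | SD, baseline-adjusted | Power |
|---|---|---|---|---|
| 0.5 | 4.86 | 89% | 4.21 | 96% |
| 0.4 | 5.32 | 83% | 4.45 | 94% |
| 0.3 | 5.75 | 77% | 4.64 | 92% |
| 0.2 | 6.15 | 71% | 4.76 | 90% |

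The planned model adjusts for baseline, so the right-hand columns apply. At ρ = 0.3 the residual variance ratio is (1 − 0.09)/(1 − 0.25) = 0.91/0.75 = 1.213, and 60/1.213 = 49.5 effective completers. That is about 25 per arm, still above 24.

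**4. Regression to the mean.** The expected shift is (1 − r) × (selected mean − unselected mean). The only means in the documents are 18.8 (Section I, Preliminary Data) and about 14 (Section VI). With an assumed retest correlation r of 0.8 or 0.7, the shift is 0.2 × 4.8 = 0.96 or 0.3 × 4.8 = 1.44 points. This is not a usable estimate: 18.8 is the mean of six women, and 14 comes from general-insomnia trials that Section VI sets aside as a different population. Whatever its size, the expected shift is the same in both randomised arms and cancels from the treatment difference.

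**The case for a change.** The best argument for acting is that the Section IV list looks complete. The same paragraph lists the PHQ-9 at Visits 1, 3 and 4, which matches the table exactly, so leaving Visit 2 out of the ISI list could be read as deliberate. The Treatment period text does not name the ISI and is not true of every scale: the table takes the pre-treatment PHQ-9 and PGI at V1.

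The choice of score could also matter in ways that the power figures miss. Women on sleep medication are asked to stop when diary tracking begins, after the telephone screen. With a 2-week recall, a telephone ISI may cover nights on those drugs. Under the missing-data rule, "Missing data will be imputed as last observation carry forward", a woman lost before V3 would have her V2 score carried forward. Set against a telephone baseline, she would show a change with no on-treatment data.

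Two things stand: the omission of Visit 2, and the absence of a named baseline visit in Section VI. The rest explains why V2 is the better baseline, and V2 is the one the table already provides. The PHQ-9 match fits a slip in a single list as well as it fits intent. For the telephone score to become baseline, staff would have to skip an assessment marked in the table, or an analyst would have to pass over the randomisation-visit score for an older screening one. Neither is likely in a trial whose visits are described at one hospital.

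**Conclusion.** No change to the plan is needed. The mismatch between Section IV and the Table of Procedures is real but clerical, and the missing definition is one that an analyst would fill correctly with the V2 score. Adding Visit 2 to the Section IV list would be an editorial tidy-up that alters neither what is collected nor how it is analysed.

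The consequence of the less likely reading is also small. The randomised comparison would stay unbiased by regression to the mean, and baseline-adjusted power would remain about 90% to 94% for assumed correlations of 0.2 to 0.4, against a planned 80%. Inflated responder proportions would affect both arms, in an analysis that Section VI labels exploratory. The power figures rest on the protocol's difference, SD and completer numbers, and on assumed correlations and an equal score SD that the documents do not give. The conclusion that V2 is the baseline rests on the text alone.
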